8.4 Response and Stable Disease Duration (RECIST 1.1 and iRECIST)

Response duration will be measured from the time measurement criteria for CR/PR or iCR/iPR (whichever is first recorded) are first met until the first date that recurrent or progressive disease is objectively documented, taking as reference the smallest measurements recorded on study (including baseline).

Stable disease duration will be measured from the time of registration/randomization until the criteria for progression are met, taking as reference the smallest sum on study (including baseline).

8.5 Prostate Response according to PCWG3 *(as defined by Scher 2016)*

All patients will be evaluable for PSA response provided follow-up PSA values are obtained to allow application of the definitions below [Bubley 1999].

Response: 50% fall in PSA from baseline maintained for ≥ 4 weeks, and without evidence of disease progression documented at time of confirmatory values.

Non Response: Failure to achieve PSA response criteria.

PSA response duration will commence on the date of the first 50% decline in PSA. The response duration ends when the PSA value increases by 50% above the nadir value, provided that the increase is at least 2 ng/mL (μ g/L) (or back to baseline).

8.5.1 *PSA Progression*
(as defined by Scher 2016)

In PSA non-responders: PSA progression is defined as the date that a 25% or greater increase and an absolute increase of 2 ng/mL (μ g/L) or more from the nadir (or baseline if no decrease from baseline is documented), which is confirmed by a second value obtained 3 or more weeks later.

In PSA responders: rise in PSA of 25% (minimum 2 ng/ml (μ g/L)) above nadir value and confirmed by a second increasing value obtained 3 or more weeks later.

Time to PSA progression will be calculated from date of randomization to date of PSA progression. If interval PSA values are collected or reported during cycle, only the end of cycle PSA (PSA collected for Day 1) will be used in response evaluation.

NOTE: Because with systemic treatment an initial rise in PSA is followed by a drop, it is recommended patients receive at least 12 weeks of therapy even if PSA is rising, provided no other evidence of progression is seen, palliative radiation is not required and protocol therapy is tolerable (see Section 10.0).

8.5.2 *Clinical Benefit*

Clinical benefit is defined for the purpose of this protocol as one of the following:

- PSA decline \geq 50%
- Complete or partial objective response
- Stable disease for \geq 12 weeks

8.5.3 *Clinical Progression*

Clinical progression is defined as the need for palliative radiotherapy, change in anti-cancer therapy, or cancer related decrease in ECOG performance status to \geq 3.

8.5.4 *Bone Disease Progression*

For the purpose of evaluation of bone disease in this study, a bone scan will be done at baseline and must be repeated every 12 weeks after randomization and at end of study, regardless if positive or negative at baseline.

For progressive disease in bone lesions, if at least 2 new bone lesions are seen by bone scan on the first post treatment scan, then these lesions are confirmed by a second bone scan done 6 or more weeks later that also shows at least 2 additional new bone lesions (2 + 2 rule) then the date of progression is the date of the first post-treatment scan.

For scans after the first post treatment scan, if 2 new bone lesions are visualized, then these lesions need to be seen on a subsequent scan confirming disease progression. If confirmed, the date of PD is the date of the first scan. In general, unequivocal progression of bone lesions will not be accepted as evidence of disease progression unless the criteria above are met and are confirmed.

Additionally, if a new bone lesion(s) are seen on the patient's CT it will also need to be confirmed with a bone scan and will ONLY be considered PD if the criteria above are met.

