2. Patients will be monitored before, during and after the first cycle infusion of tremelimumab and durvalumab with assessment of vital signs to be collected \leq 30 minutes prior to start of infusion then every 30 \pm 5 minutes during infusion; a 1-hour observation period is recommended after the tremelimumab. Assessment of vital signs in subsequent cycles is required prior to the start of the infusion, and then as clinically indicated. If no clinically significant infusion reactions are observed during or after the first cycle of tremelimumab+durvalumab therapy, subsequent infusion observation periods can be at the investigator's discretion.
3. Pre-treatment blood draws and physical exams may be done one working day prior to treatment if necessary (e.g. Friday for treatment on Monday, or to accommodate holidays). In order to ensure that nadir counts are not missed, every effort should be made to do interim blood draws within 24 hours of the day specified in the protocol. If a patient shows an AST or ALT $\geq 3 \times$ ULN together with total bilirubin $\geq 2 \times$ ULN, refer to Appendix II for further instructions on cases of increases in liver biochemistry and evaluation of Hy's Law. These cases should be reported as SAEs if, after evaluation, they meet the criteria for a Hy's law case or if any of the individual liver test parameters fulfill any of the SAE criteria.
4. Required at 4 weeks. Then every 3 months thereafter to follow abnormal lab results felt related until resolved to \leq grade 2.
5. It is preferable that both amylase and lipase parameters are assessed. For sites where only 1 of these parameters is routinely measured then either lipase or amylase is acceptable as long as the same one is followed throughout.
6. At least three previous PSA values with the interval between of ≥ 4 weeks, should be recorded for the patient to estimate doubling time as well as one prior to registration.
7. PSA should also be done at the end of the last cycle.
8. All patients at 4 weeks. For patients without PSA progression, repeat every 4 to 8 weeks until progression or until new systemic therapy is initiated.
9. Free T3 and free T4 will be measured if TSH is abnormal.
10. Patients with CR/iCR or PR/iPR or equivocal PD (pseudoprogression)/iUPD should have scans repeated after 4 weeks, but no more than 8 weeks, to confirm response.

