13.0 STATISTICAL CONSIDERATIONS

13.1 Objectives and Design

The primary objective of this randomized, open-label, and non-comparative phase II trial is to determine the objective response rate in patients with metastatic castration resistant prostate cancer treated with durvalumab alone or in combination with tremelimumab. Secondary objectives include determining the PSA response rate, evaluating the time to progression based on measurable disease, bone progression or PSA, and the toxicity and tolerability in patients receiving durvalumab ± tremelimumab. Patients will be randomized in 1:1 ratio to receive durvalumab alone or in combination with tremelimumab. Between 24 and 74 patients will be enrolled.

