13.2 Primary Endpoints and Analysis

The primary endpoint of this study is the objective response rate, using iRECIST criteria defined in Section 8. Objective response rate using RECIST 1.1 will also be reported. 95% confidence interval for objective response rate in both definitions will be calculated.

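### Section 8.5 ties PSA evaluability to follow-up PSA and section 13 gives no other denominator, so a PSA response rate in evaluable patients can equal or exceed, but never fall below, the all-treated rate

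*Combined protocol and SAP*

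**What the plan says.** Section 8.5 opens with an evaluability condition: "All patients will be evaluable for PSA response provided follow-up PSA values are obtained to allow application of the definitions below". It then defines response as a "50% fall in PSA from baseline maintained for" at least 4 weeks, without disease progression at the confirmatory value. The other class is "Non Response: Failure to achieve PSA response criteria". Nothing is said about a patient with no usable follow-up value.

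In section 13.1, "Secondary objectives include determining the PSA response rate" gives the endpoint its status. Section 13.2 deals only with objective response: "95% confidence interval for objective response rate in both definitions will be calculated". No part of section 13 states which patients form the denominator of the PSA response rate or how missing PSA is handled.

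The section 5.0 flowsheet puts PSA before study and on Day 1 of each cycle. Its footnotes add that "PSA should also be done at the end of the last cycle" and that all patients have a PSA 4 weeks after therapy. After that, "For patients without PSA progression, repeat every 4 to 8 weeks until progression" or until new systemic therapy. Section 10.4 has all patients seen 4 weeks after completing treatment.

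**The concern.** Whether a patient is evaluable depends on data collected after treatment starts. The patients most likely to have no follow-up PSA are those who die, withdraw or are lost soon after the first dose. None of them has shown a response, so the gap is plausibly related to outcome. Leaving them out takes non-responses from the denominator and nothing from the numerator.

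Elsewhere the protocol guards against this. Section 8.1.2 keeps patients with objective progression before the end of cycle 1 evaluable for objective response; section 8.5 has no similar clause for PSA.

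What is at stake is how a named secondary endpoint is read. If the denominator is not fixed in advance, two analysts could report different PSA response rates from the same data, and in an open-label trial the choice could be made after the results are seen.

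**Working it through.** **The plan's own figures.** No figure is given for the PSA response rate. The only design calculation is the objective response design in section 13.3: 5% against 20%, alpha and beta both 0.1, 12 then 37 patients per arm, expand on 1 or more responses, positive on 4 or more. An exact binomial search for the Simon optimal design returns the same plan (stop at 0/12, reject at 3/37 or fewer), with alpha 0.0935, power 0.9024 and probability of early stopping under 5% of 0.95^12 = 0.540. No PSA quantity enters it, so the PSA rule cannot alter the stage 1 or final decision.

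**Who can lack follow-up PSA.** Take a patient who stops after one 4-week cycle. The schedule gives a PSA at the end of that cycle (about week 4). The post-treatment visit, which Appendix IV times from the end of the last cycle, gives another at about week 8. That is two values about 4 weeks apart, enough to apply the response definition. Patients with no usable value are therefore mainly those who die early, withdraw, are lost to follow-up or miss draws.

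**Formula.** Let N be the treated patients in an arm, R the PSA responders and m the patients with no usable follow-up PSA.

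- Rate with missing counted as non-response: R/N
- Rate in evaluable patients only: R/(N−m)
- Ratio: N/(N−m)
- Difference: R·m / [N(N−m)]

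The difference is zero if R = 0 or m = 0, positive otherwise, and never negative.

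**Numbers.** N = 37 and N = 12 come from section 13.3. R and m are assumptions, because the documents give neither.

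| N | R | m | R/N | R/(N−m) | Ratio | Difference (points) |
|---|---|---|---|---|---|---|
| 37 | 5 | 2 | 5/37 = 13.5% | 5/35 = 14.3% | 1.057 | 0.8 |
| 37 | 5 | 4 | 13.5% | 5/33 = 15.2% | 1.121 | 1.6 |
| 37 | 5 | 6 | 13.5% | 5/31 = 16.1% | 1.194 | 2.6 |
| 37 | 7 | 2 | 7/37 = 18.9% | 7/35 = 20.0% | 1.057 | 1.1 |
| 37 | 7 | 6 | 18.9% | 7/31 = 22.6% | 1.194 | 3.7 |
| 12 | 1 | 2 | 1/12 = 8.3% | 1/10 = 10.0% | 1.200 | 1.7 |
| 12 | 4 | 1 | 4/12 = 33.3% | 4/11 = 36.4% | 1.091 | 3.0 |
| 12 | 4 | 2 | 33.3% | 4/10 = 40.0% | 1.200 | 6.7 |

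For scale, the exact 95% interval for 5/37 is 4.5% to 28.8%, so the shift at 37 per arm is small beside the sampling error. It is relatively larger in an arm that closes at 12.

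**The case against.** The strongest reply is that the schedule leaves few patients without follow-up PSA, that the trial is non-comparative so no between-arm PSA test is distorted, and that a rate in evaluable patients is a recognised choice which readers can convert if the counts are reported. All of that stands, and it limits the size of the point. It does not supply a denominator or say how a patient without usable values is classified.

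Four stronger readings are tempting, and the documents support none of them.

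- A reader might infer that section 8.5 contradicts itself, because a patient without PSA literally meets "Failure to achieve PSA response criteria". That line follows the evaluability sentence and can be read as classifying evaluable patients only. The patients without values are then unclassified, which is a gap and not a contradiction.
- A reader might infer from the 4-week cycles that anyone leaving before about week 8 has a single follow-up value. The end-of-last-cycle and post-treatment draws show otherwise for patients who attend. The sentence in 8.5.1 restricting response evaluation to Day 1 values concerns interval samples within a cycle and does not clearly exclude post-treatment values. One value without a 50% fall also already shows that response was not reached at that point; single-value patients are ambiguous mainly when that value shows a fall awaiting confirmation.
- A reader might infer that the PSA set is smaller than the objective response set. Evaluability under 8.1.2 needs one cycle plus disease re-evaluation, or objective progression before the end of cycle 1. On-treatment imaging is every 12 weeks against every 4 for PSA, so a patient leaving between the first follow-up PSA and the first scan could be evaluable for PSA and not for objective response.
- A reader might take upward bias as established. No section says outright that the rate is computed in evaluable patients. That is the ordinary meaning of the term and the only rule available, but the inflation remains conditional.

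**Conclusion.** The point holds in conditional form. As written, section 8.5 makes PSA evaluability depend on follow-up PSA, and nothing in section 13 overrides it. If the rate is reported in evaluable patients, it will equal or exceed the rate in all treated patients, and it will exceed it by the factor N/(N−m) once an arm has at least one responder and one patient without usable values.

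This rests on three assumptions: that the evaluable set is used as the denominator, that patients without usable PSA are properly counted as non-responders (plausible for early death, withdrawal or loss, but not stated), and that R and m lie in the range shown. With 5 responders in 37 the excess is 0.8 to 2.6 percentage points for 2 to 6 patients left out. The true m is unknown and, given the PSA schedule, may be small. The primary endpoint and the two-stage rules do not depend on it. This is a cheap improvement to a secondary endpoint and does not call the design into question.

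**What to change.** Replace the evaluability sentence in section 8.5 with: *The PSA response rate is calculated in all treated patients with a baseline PSA; patients without follow-up or confirmatory PSA values are counted as non-responders.* Report the rate in patients with follow-up PSA as a sensitivity result, with both denominators shown.

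The change is one sentence, uses data already scheduled and needs no extra visits or patients. The reported PSA response rate may be slightly lower, partly because a 50% fall that is never confirmed will count as non-response. The change should be made before the PSA data are analysed.

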5.0 PATIENT EVALUATION FLOWSHEET: PRE-TREATMENT, ON STUDY, AND AFTER TREATMENT

All patients entered on study must be evaluated according to the schedule outlined below with documentation submitted according to the schedule in Appendix IV.

Required Investigations	Pre-study (≤7 days prior to randomization)	Day 1 each cycle, and as clinically indicated	Every 12 weeks after randomization	4 weeks after completion of protocol therapy	3 month follow-up (only required for pts without confirmed PD and ongoing toxicities ¹)	6 month follow-up (required for all patients with confirmed PD)
History and Physical Exam						
Including: height, weight, BSA, performance status, clinical tumour measurements (if applicable)	X	X		X		
Blood pressure, heart rate, temperature	X	X ²		X		
Laboratory Procedures/Assessments³						
CBC, differential, platelets	X	X		X ⁴	X ⁴	
PTT, PT/INR (if on anticoagulants)	X	X		X ⁴	X ⁴	
Serum creatinine, bilirubin, AST, ALT, ALP, LDH, albumin, glucose, amylase ⁵ , lipase ⁵ , electrolytes (potassium, calcium, magnesium)	X	X		X ⁴	X ⁴	
PSA	X ⁶	X ⁷		X ⁸	X ⁸	
TSH ⁹	X	X				
Testosterone (to confirm biochemical castration only)	X					
Radiology^{10,11}						
Chest/abdomen/pelvis CT scan Other scans as necessary to document disease ¹²	X (within 28 days prior to randomization or 35 if negative)		X	X	X	
Bone Scan ^{12,13}	X (within 28 days prior to randomization or 35 if negative)		X	X	X (if positive at baseline and does not yet have confirmed PD)	
Other Investigations						
Urinalysis ¹⁴	X					
LVEF ¹⁵	X (within 28 days prior to randomization)					
Adverse Events	X	Continuously		X	X ¹	
Survival/Anti-cancer Treatment Follow-up						X
Correlative Studies (mandatory)						
Fresh tumour biopsy ¹⁶	X					
Archival Tumour Tissues	X					
Blood Collection	X ¹⁷			X ¹⁸		

footnotes on next page ...

1. Every three months thereafter to follow adverse events felt related until resolved to \leq grade 2.

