11. To ensure comparability, baseline scans and subsequent scans to assess response must be performed using identical technique (i.e. scans performed immediately following bolus contrast administration using a standard volume of contrast, the identical contrast agent, and preferably the same scanner).
12. Maintain schedule every 12 weeks even if cycles are delayed.
13. Bone scan is required and must be repeated every 12 weeks and end of study, regardless if positive or negative at baseline, as well as when clinically indicated. If NEW bone lesion(s) are noted on the patient's bone scan, see Section 8.5.4 for details.
14. Only as clinically indicated after baseline
15. Only if significant cardiac history (see section 4.2.7)
16. Fresh Biopsy is mandatory for all patients after consent but prior to randomization, see Section 12.0.
17. To be collected after randomization and prior to cycle 1 treatment.
18. To be collected at end of treatment/disease progression

5.1 Follow-up for Ineligible or Patients That Go Off Study Prior to Starting Protocol Therapy

The follow-up requirements for ineligible patients/patients who have received no protocol therapy prior to going off study include submission of the Baseline Report plus an End of Treatment Report. Data submission for ineligible participants who have received at least one dose of protocol therapy should be followed according to the protocol to allow for treatment and adverse event assessment.

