7.1 Durvalumab and Tremelimumab Treatment Plan

7.1.1 Drug Administration

When durvalumab is given with tremelimumab, tremelimumab will be administered first. Durvalumab infusion will start approximately 1 hour after the end of tremelimumab infusion.

One cycle will be defined as 4 weeks. Tremelimumab will only be given for the first 4 cycles.

Arm	Agent(s)	Dose	Route	Duration	Schedule
1 & 2	Durvalumab	1500 mg	IV	60 min	Day 1 every 4 weeks
1	Tremelimumab	75 mg	IV	60 min	Day 1, cycles 1-4

Patients with a body weight of less than or equal to 30 kg should be dosed using a weight based dosing schedule. See Section 3.3.

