7.1.4 Dose Adjustments

The major toxic effects of durvalumab or tremelimumab which are anticipated to limit dosing are hypersensitivity/ infusion related reactions and possible class related immune related AEs, based on the mechanism of action of durvalumab ± tremelimumab leading to T-cell activation and proliferation. Potential immune related AEs include pneumonitis, hepatitis, diarrhea/colitis and intestinal perforation, endocrinopathies (thyroiditis, hypo and hyperthyroidism, adrenal insufficiency, hypophysitis/hypopituitarism diabetes insipidus and Type 1 diabetes mellitus), nephritis, rash/dermatitis, pancreatitis, myocarditis, myositis/polymyositis and rare/less frequent irAEs including neuromuscular toxicities such as myasthenia gravis and Guillain-Barre syndrome. Other inflammatory responses that are rare with a potential immune-mediated etiology include, but are not limited to, pericarditis, sarcoidosis, uveitis and other events involving the eye (e.g. keratitis and optic neuritis), skin (e.g. scleroderma, vitiligo and pemphigoid), hematological (e.g. hemolytic anemia and immune thrombocytopenic purpura) and rheumatological (e.g. polymyalgia rheumatic and autoimmune arthritis) events, vasculitis, non infectious encephalitis or non infectious meningitis. It is possible that events with an inflammatory or immune mediated mechanism could occur in nearly all organs.

The guidelines that outline dose adjustments for these toxic effects can be found in Appendix II. If a patient experiences several adverse events and there are conflicting recommendations, please use the recommended dose adjustment that requires the greatest dose hold or discontinuation. Adverse events will be graded using the NCI Common Terminology Criteria for Adverse Events (CTCAE) (see Appendix V).

Dose adjustments (slowing/interruption of infusion rate, omission of a dose, or permanent discontinuation) will be made for hematologic and other adverse events.

If the infusion cannot be administered, it should be omitted until the next planned infusion.

The next cycle should not be given until the laboratory criteria in Section 4.1.9 are met and resolution of all drug related toxicity to \leq grade 2. Discuss with CCTG if asymptomatic/not felt to be clinically significant.

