8.6 Methods of Measurement

The same method of assessment and the same technique should be used to characterize each identified and reported lesion at baseline and during follow-up. Assessments should be identified on a calendar schedule and should not be affected by delays in therapy, which may be treatment arm dependent. While on study, all lesions recorded at baseline should have their actual measurements recorded at each subsequent evaluation, even when very small (e.g. 2 mm). If it is the opinion of the radiologist that the lesion has likely disappeared, the measurement should be recorded as 0 mm. If the lesion is believed to be present and is faintly seen but too small to measure, a default value of 5 mm should be assigned. For lesions which fragment/split add together the longest diameters of the fragmented portions; for lesions which coalesce, measure the maximal longest diameter for the “merged lesion”.

- 8.6.1 **Clinical Lesions.** Clinical lesions will only be considered measurable when they are superficial and ≥ 10 mm as assessed using calipers (e.g. skin nodules). For the case of skin lesions, documentation by colour photography including a ruler to estimate the size of the lesion is recommended. If feasible, imaging is preferred.
- 8.6.2 **Chest X-ray.** Chest CT is preferred over chest X-ray, particularly when progression is an important endpoint, since CT is more sensitive than X-ray, particularly in identifying new lesions. However, lesions ≥ 20 mm on chest X-ray may be considered measurable if they are clearly defined and surrounded by aerated lung.
- 8.6.3 **CT, MRI.** CT is the best currently available and reproducible method to measure lesions selected for response assessment. This guideline has defined measurability of lesions on CT scan based on the assumption that CT slice thickness is 5 mm or less. When CT scans have slice thickness greater than 5 mm, the minimum size for a measurable lesion should be twice the slice thickness. MRI is also acceptable in certain situations (e.g. for body scans). Other specialized imaging or other techniques may also be appropriate for individual case [Eisenhauer 2009]. For example, while PET scans are not considered adequate to measure lesions, PET-CT scans may be used providing that the measures are obtained from the CT scan and the CT scan is of identical diagnostic quality to a diagnostic CT (with IV and oral contrast).

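### On-treatment PSA lacks the calendar rule given to imaging, so a dose hold that moves Day 1 can date PSA progression late

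*Combined protocol and SAP*

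**What the plan says.** Section 5.0 places on-treatment PSA in the flowsheet column headed "Day 1 each cycle, and as clinically indicated". Section 7.1.1 fixes the nominal interval: "One cycle will be defined as 4 weeks". Section 8.5.1 defines the endpoint ("Time to PSA progression will be calculated from date of randomization to date of PSA progression") and then says of values gathered within a cycle that "only the end of cycle PSA (PSA collected for Day 1) will be used in response evaluation". For PSA non-responders, progression is a qualifying rise "which is confirmed by a second value obtained 3 or more weeks later".

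Imaging is handled differently. Footnote 12 of the flowsheet, attached to the CT and bone scan rows, reads "Maintain schedule every 12 weeks even if cycles are delayed". Section 8.6 gives the reason: assessments follow a calendar and "should not be affected by delays in therapy, which may be treatment arm dependent". The PSA row carries footnotes 6 to 8 only. Footnote 7 adds a PSA at the end of the last cycle. Footnote 8 puts PSA on a calendar once treatment has stopped: at 4 weeks, then every 4 to 8 weeks.

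Section 7.1.4 makes two statements about a dose that cannot be given on time. One is "The next cycle should not be given until the laboratory criteria in Section 4.1.9 are met", with drug-related toxicity also required to have settled to grade 2 or less. The other is that the infusion is skipped and treatment picks up at the next planned one. Footnote 12 and Section 7.3.1 speak of delays. None of these places says whether Day 1, and the PSA attached to it, moves.

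**The concern.** The protocol recognises that assessments tied to dosing can be distorted by holds, and that the distortion may differ between arms. It removes the problem for scans and leaves it for on-treatment PSA. The Day 1 sentence adds to this: a PSA drawn because it was clinically indicated during a hold would be collected and then set aside. If Day 1 moves, no countable value exists until dosing resumes, and a rise that has already qualified is dated to the resumption day.

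Time to PSA progression comes from a stated secondary objective (Sections 1.2 and 13.1). Section 13.1 lists it beside progression in measurable disease and in bone, so components of one objective would be observed on different clocks. Sites could also read the omit and delay statements differently. A PSA that was never drawn during a hold cannot be recovered at analysis.

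**Working it through.** **The plan's own figures.** No figure is given for PSA endpoints. The only design calculation is the Simon two-stage design in Section 13.3 (12 then 37 per arm, 5% against 20%). It reproduces: exact alpha 0.0935, power 0.9024, with stopping bounds 0/12 and 3/37. It uses objective response only, so nothing below affects it.

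**Inputs from the documents.** The nominal PSA interval is 28 days (Section 7.1.1), and only the Day 1 value counts (Section 8.5.1). Progression is read as dated to the first qualifying rise, with confirmation 3 or more weeks later.

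**Assumed inputs.** The documents give neither a hold rate nor a hold length. Let f be the fraction of cycles in which Day 1 moves and d the number of days it moves. I take f from 5% to 30% and d from 7 to 28 days. The 22% row borrows the related grade 3/4 event rate in Section 2.0 (4/18) as an anchor only; it is not a hold rate.

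**Formula.** If the gap between counted PSA values is L, the mean delay from the true threshold crossing to the next counted value is E[L²] / (2 E[L]). Here L = 28 with probability 1 − f and 28 + d with probability f.

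- Calendar PSA, no movement: 28² / (2 × 28) = 14.0 days.
- f = 10%, d = 14: E[L] = 0.9 × 28 + 0.1 × 42 = 29.4; E[L²] = 0.9 × 784 + 0.1 × 1764 = 882; delay = 882 / 58.8 = 15.0 days, an excess of 1.0.
- f = 30%, d = 28: E[L] = 0.7 × 28 + 0.3 × 56 = 36.4; E[L²] = 0.7 × 784 + 0.3 × 3136 = 1489.6; delay = 1489.6 / 72.8 = 20.46 days, an excess of 6.46.

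Mean delay in days, with the excess over the calendar schedule in brackets:

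| f | d = 7 | d = 14 | d = 28 |
|---|---|---|---|
| 5% | 14.22 (+0.22) | 14.51 (+0.51) | 15.33 (+1.33) |
| 10% | 14.43 (+0.43) | 15.00 (+1.00) | 16.55 (+2.55) |
| 22% | 14.91 (+0.91) | 16.08 (+2.08) | 19.05 (+5.05) |
| 30% | 15.22 (+1.22) | 16.74 (+2.74) | 20.46 (+6.46) |

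**Simulation check.** Crossing times were exponential with true medians of 2, 3, 4 and 6 months, f was 10% to 30% and d was 14 to 28 days. The mean shift was 1.0 to 6.9 days. The recorded medians were 84, 112, 140 and 196 days, the same with and without holds in every scenario, because detection falls largely on a 28-day grid.

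**The other reading.** If a held dose is omitted, Day 1 stays on the 4-week grid and PSA is still drawn then, L is always 28 and the excess is 0 days.

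**The case against.** The best case against the point is that the lengthening is conditional and may not occur. Section 7.1.4 expressly provides for omission, which can leave Day 1 where it was planned. A reader might infer that every hold lengthens time to PSA progression; the text does not support that.

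A second argument concerns the draw due at the end of a 4-week cycle when the next dose is then held. Section 8.5.1 equates the end-of-cycle value with the Day 1 value, and blood is taken at that point to decide on dosing, so the draw is plausibly counted. The gap of 28 + d then splits into 28 and d. With d = 28 both parts are 28 and the mean delay is 28 / 2 = 14.0 days, as on the calendar. For holds up to 28 days the excess in the table disappears, and only longer holds leave a wider gap. A reader might also infer that late confirmation adds to the error. It has little effect: the date is set by the first rise and the confirmation window has no upper limit.

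Third, Section 8.6 speaks of assessments in general and includes tumour markers (8.6.7), so its calendar principle can be read to cover PSA. The Day 1 sentence refers to response evaluation, and its application to progression is inferred from its position in 8.5.1.

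These arguments limit the size and certainty of the effect. They do not remove the gap. The favourable outcome depends on each site choosing one of several readings. If 8.6 does govern PSA, it conflicts with the Day 1 schedule and counting rule whenever Day 1 moves.

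**Conclusion.** The point holds in conditional form. On-treatment PSA lacks the protection given to imaging, and if a hold moves Day 1 a stated counting rule can date progression late, by up to the length of the hold in an affected patient. On average the effect is small: about 0.2 to 6.5 days over the assumed range, no change in simulated medians, and zero under the readings described above. These figures assume that holds occur independently across cycles, that nothing between delivered Day 1 draws is counted, and that the Day 1 rule covers progression as well as response.

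A reader might infer that the bias falls mainly on the combination arm. That direction is plausible: Section 2.0 expects added toxicity and Section 8.6 allows for arm-dependent delay. But no hold rates by arm are given, and tremelimumab is confined to cycles 1 to 4. Patients who stop treatment move to calendar PSA. The event rates in Section 2.0 cannot fill the gap, because related grade 3/4 events for the combination and immune-related events for single agents are different events, and neither is a rate of holds. Nor does Section 7.1.5 supply a hold length: its steroid taper of 4 weeks or more is not stated as a period without dosing.

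A reader might also infer that the result would favour one arm in a comparison. Section 13.1 calls the trial non-comparative, and go/no-go rests on objective response. What is affected is each arm's descriptive estimate of a secondary endpoint. This is a cheap improvement, not a threat to the trial's conclusions.

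**What to change.** In Section 5.0, schedule PSA every 4 weeks from randomization while on treatment, whether or not the infusion is given, and add a PSA footnote equivalent to footnote 12.

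In Section 8.5.1, replace the Day 1 sentence with wording such as: *PSA values from the scheduled 4-weekly calendar visits are used for both PSA response and PSA progression, regardless of dose delay or omission; other unscheduled values are not used.*

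The omitted and delayed wording in Section 7.1.4, Section 7.3.1 and footnote 12 must be reconciled. No view is taken here on which handling of a held dose is right; the PSA rule above works under either.

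The cost is a change of wording and, at most, an occasional extra PSA tube during a hold. Recorded time to PSA progression may be slightly shorter than under the present text.
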